The Hepalbin[™]-Adsorbent is a nano-structured carbon filter that removes up to 95% of the industrial stabilisers octonoic acid (caprylate) and N-acetyltryptophanate from commercially available pharmaceutical albumin preparations. These stabilisers are associated with the binding sites of albumin, thus reducing albumin functionality and binding capacity. While in healthy individuals, these stabilisers are metabolized by the liver and have a very short half-life, this is significantly prolonged in liver disease potentially causing accumulation of these materials. The use of Hepalbin[™]-Adsorbent for albumin transfusion indicated that there may be clinical benefit to stabilizer removal in patients with decompensated liver disease in a small controlled study [16].

-

SepteX and oXiris filters are the brandnames of the filters and have no further model specification.

⁸ In the majority of hospitals most recent versions of both Prismaflex and software are available. In Austria the Model ref: 60 23014700 can be in used in Graz; the software version installed is version 8.1

Clinical Investigation Plan	CIP YAQ-002	Version: 7.0 10 October 2019
-----------------------------	-------------	------------------------------

2.2 Definitions.

Screen failures:

- The patient does not meet one or more criteria, which are assessed after the patient (and/or consultee if applicable) signed the Informed Consent; patient can re-enter the study later if at that moment all inclusion criteria and no exclusion criteria are met. Patient informed consent remains valid until end of the study or until withdrawal from the study.
- 2. Patient who did not start dialysis before the end of DAY 1 if randomized to the DIALIVE treatment arm, is considered a screen failure; such a patient does not have to resign a consent form, but can re-enter the study via de novo demonstration of compliance with the in- and exclusion criteria.

Patient withdrawal: a patient (or the consultee if applicable) can withdraw consent at any time. No further clinical data can be collected as of that moment; the data collected prior to that moment, remain part of the clinical study.

Patient exclusion: a patient is considered excluded from the study (and from re-entering into the study):

- 1. Upon demonstration of more than 2 interuptions of more than 24 hrs between subsequent dialysis sessions and within the first 10 day time period after randomization (DIALIVE arm);

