- 2. If the clinical condition of a patient meets one or more study stopping criteria.

Patients considered to be a 'screen failure' or 'excluded' will remain in study for a minimum follow up period of 28 days.

Standard definitions: definitions for DIALIVE organ failure and ACLF grading per the CLIF-C OF scoring system, Lille score, and others, are given in Appendix 1-2.

Hepatic Encephalopathy (HE): determination of HE as part of ACLF grading will be based upon clinical assessment and graded as per the West Haven criteria. However, if there is ambiguity or observer variability, an EEG may be sought by the PI for supportive evidence. This is particularly relevant for grade 1 HE which may not be consistenly reproducible using the West Haven criteria, and as such is now included as part of the covert HE spectrum along with minimal HE often requiring psychometric tests or EEG for diagnosis

Specific therapy such as corticosteroids for alcoholic hepatitis can be used if a patient is already within the study and these have not been trialed previously and as long as clinical justification and rationale is clearly documented. This applies to patients in both SOC and the DIALIVE arm. For other indications of steroid use such as potential relative adrenal insufficiency, it should precede a short synacthen test, particularly in patients who are haemodynamically stable, to establish this diagnosis.

Standard of Care (SOC) is defined as the standard medical and nursing management of patients with ACLF Grades 1 and 2 as per local practices. Medical intervention is to be guided by the treating physician taking into account the overall clinical picture, precipitating event, and the nature and severity of organ dysfunction. The interventions may include (but not limited to) the supportive management with fluid therapy, including albumin therapy where indicated, antibiotics for suspected or confirmed infections, nutrition, bowel management, thromboprohylaxis, and organ system support including the use of terlipressin as splanchnic vasopressor and for cardiovascular support where indicated, oxygen and non-invasive respiratory support, laxatives and non-absorbable antibiotics for hepatic encephalopathy, and dialytic therapy for renal failure. SOC may also include urgent liver transplantation as per local practices.

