Patients presenting with, or developing during the study period, severe actue renal failure requiring renal support, will receive continuous renal replacement therapy (CRRT) as per standard local practices. This would apply to subjects in both SOC and DIALIVE arms. For those in the DIALIVE arm, the same vascular catheter which is used for DIALIVE treatment may be used for CRRT following the completion of the DIALIVE treatment session. It is however envisaged

that increased intensity of dialysis component in the DIALIVE system (from 1lit/hr to 1.5lit/hr) and allowance for fluid removal in the new protocol may delay or remove altogether the need for CRRTin these situations. The decision for additional CRRT would depend on clinical situation and will be taken by the site PI.

DIALIVE arm consists of standard of care (defined above), plus DIALIVE treatment.

A DIALIVE treatment session denotes treatment for the day, whereas A DIALIVE treatment cycle refers to the total number of treatment days.

A DIALIVE treatment **session** = A minimum, cumulative duration of 8 to 10 hrs (± 30 min) of the DIALIVE treatment, thus allowing for breaks which may be planned (for example patients needing to go for imaging) or unplanned (device clotting, issues with vascular access or other any other unplanned reasons). A break within a treatment session (consisting of a cumulative time longer than 4hrs), or a cumulative duration of less than 8 hrs of dialysis during one day constitutes a session failure for that day. A session failure will require to restart the dialysis session within 24 hrs after the end of the previous session and will reset the start of the dialysis cycle.

A DIALIVE treatment **cycle**= Consists of 3 consecutive days of 8-10 hrs of DIALIVE treatment sessions on each day within the 10 day window period. A break of more than 24hrs between each treatment session will require a new baseline (i.e. a new treatment cycle commenced). A second failed treatment session within the 10 day window period would result in patient exlusion. The patient must have completed one successful treatment cycle within the 10 day window period to be considered evaluable.

Day of randomization constitutes study Day 0.

The first treatment session (DIALIVE arm only) must commence before the end of study Day 1. As such, dialysis might also start on the day of randomization which might created confusion as 'the first day of dialysis' then concurs with DAY 0 of the study schedule.

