5.2. Investigational device exposure

For the randomization an Interactive Wireless Randomization System (IWRS) is used, which is linked to the study data base. Randomization is automatically assigned through the IWRS system. Patients are randomised to either the DIALIVE or SOC arm in a 1:1 ratio.

¹¹ The prismaflex platform will be provided by Yaqrit to those sites that do not have access to such haemofiltration machines. The machine will remain the property of Yaqrit Ltd during and after the study. A mainenance agreement in such circumstances will be established with each institution.

Patients will be assigned into five (5) Cohorts. Each cohort will consist of six (6) patients (3 DIALIVE: 3 SOC). If there are dropouts in any of the following cohorts during the study period, patients will be replaced in each of the cohorts described below to reach the appropriate number of 6 evaluable patients in each cohort.

Cohort 1: including 3 control and 3 DIALIVE treated patients. Cohort 2: including 3 control and 3 DIALIVE treated patients. Cohort 3: including 3 control and 3 DIALIVE treated patients. Cohort 4: including 3 control and 3 DIALIVE treated patients. Cohort 5: including 3 control and 3 DIALIVE treated patients.

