5.3.4. Point of enrolment

Patients will be recruited through in-patient wards across multiple European centres. Approximately one (1) patient every four (4) months per centre will be recruited with an estimated three (3) patients per centre in total, although competitive recruitment will be utilised. This recruitment strategy is based upon the data accumulated during the performance of the CANONIC study [5].

Following consent and confirmation of eligibility, patients will be randomised electronically via the eCRF . The site will be issued with the subject ID number and informed of their treatment arm. Patients will be deemed enrolled at the point of randomization (Day 0).

5.3.5. Total expected duration of the clinical investigation.

The total duration of the study will be approximately 39 months.

5.3.6. Expected duration of each subject's participation.

After signing the Informed Consent, the patient can be screened for compliance with the in/exclusion criteria for up to 3 days. Patients from cohort 1, 2 and 3 are followed for 28 days, those from cohort 4 and 5 for 90 days.

Patients will be randomized on study day 0 followed by a maximum treatment window period of 10 days (DIALIVE arm). All patients will be intensively followed during the initial 28 days post-randomization and complete the study after completion of study day 28 (cohort 1, 2 and 3) or day 90 (cohort 4 and 5)...

5.3.7. Number of subjects included in the clinical investigation.

30 evaluable subjects will be randomised to receive either standard of care (SOC) or treatment with DIALIVE (1:1 randomisation).

As this is a first-in-man trial, and no hypothesis is to be tested, the sample size is arbitrarily set to obtain adequate information in a small patient population. This reduces the total number of patients exposed to potential study related risks while allowing the investigators to learn maximally from this potential treatment for ACLF-patients for which no alternative

Clinical Investigation Plan	CIP YAQ-002	Version: 7.0 10 October 2019
-----------------------------	-------------	------------------------------

treatment exists and the Data Safety Monitoring Board to make appropriate decisions on study (dis)continuation by comparing occurrence of adverse events between control and treatment arms in each of the 5 cohorts of patients.

5.3.8. Estimated time needed to select this number (i.e. enrolment/recruitment period).

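### A patient already randomised to DIALIVE who has not started dialysis by the end of Day 1 becomes a screen failure and may re-enter, and the protocol does not say whether the first allocation stands

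*Protocol*

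**What the plan says.** Section 2.2 lists two kinds of screen failure. The first is a patient found after consent not to meet a criterion. The second arises after allocation, in a patient randomised to DIALIVE whose dialysis has not begun by the end of Day 1. That patient "is considered a screen failure; such a patient does not have to resign a consent form, but can re-enter the study via de novo demonstration". What must be shown again is eligibility.

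Section 5.3.4 places enrolment earlier: "Patients will be deemed enrolled at the point of randomization (Day 0"). It also gives the order of steps: "Following consent and confirmation of eligibility, patients will be randomised electronically via the eCRF". The site is then told the arm. Section 2.2 adds that "Day of randomization constitutes study Day 0", and it sets the deadline for the first session, before the end of Day 1, for the DIALIVE arm only.

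On allocation, section 5.2 says: "Patients are randomised to either the DIALIVE or SOC arm in a 1:1 ratio". It sets five cohorts of six, three per arm. Section 5.1 states that the study is open label. Section 4.2 gives the purpose of randomisation as unbiased, balanced data from the two arms. Section 5.1.7 replaces screen failures to keep cohorts even. Section 2.2 keeps them under observation: "Patients considered to be a 'screen failure' or 'excluded' will remain in study for a minimum follow up period of 28 days". Section 6 bases all analyses on randomised patients who received at least one treatment.

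**The concern.** Screening ends at randomisation. Here a randomised, enrolled patient is sent back to screening because of something that did or did not happen after the arm was known, and then allowed in again. The deadline that triggers this exists in one arm only. What happens to the first allocation is left open.

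The primary endpoint is the percentage of patients with an SAE between Day 1 and Day 10, set out by arm, and the DSMB compares the arms cohort by cohort. If membership of an arm can depend on events after allocation, the two percentages no longer describe groups formed by chance alone. Failure to start need not be random: section 2.2 requires transfer to intensive care or similar, an arterial line, a dialysis catheter and a central line before the first session. No deliberate misuse is needed for non-starters to differ from starters.

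**Working it through.** **Step 1. Does re-entry mean a new allocation?**
- Re-entry requires eligibility to be shown afresh (2.2).
- Confirmed eligibility is followed by electronic randomisation, with no exception for re-entrants (5.3.4).
- DIALIVE must start before the end of Day 1, and Day 0 is the day of randomisation (2.2). A re-entrant has missed that deadline and can meet it only with a new Day 0, hence a new randomisation.
- No section says that the first allocation is kept.

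A second allocation is thus the natural reading, but it is inferred. On the other reading, the DIALIVE arm gains patients who have met the criteria twice, a filter that this rule does not apply to SOC patients. Both readings disturb the comparison.

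**Step 2. Design figures.** 5 cohorts x 6 = 30 patients and 5 x 3 = 15 per arm, which agrees with the stated 30. The sample size is described as arbitrary, so there is no power calculation to reproduce.

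**Step 3. Weight of one patient.** Overall: 1/15 = 6.7 percentage points of an arm's SAE percentage. Within a cohort: 1/3 of an arm, or 33 points.

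**Step 4. Effect on the mix of patients.** The document gives no non-start rate. Let q be the assumed share of DIALIVE allocations not started in time. Assume that each such patient requalifies, is redrawn once at a flat 50%, and starts if drawn to DIALIVE again.
- Final DIALIVE share = 0.5(1 - q) + 0.25q
- Share of final SOC patients first allocated to DIALIVE = 0.25q / (0.5 + 0.25q)

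| q (assumed) | Expected non-starters among 15 | DIALIVE share | SOC patients first allocated to DIALIVE |
|---|---|---|---|
| 5% | 0.75 | 48.8% | 2.4% |
| 10% | 1.5 | 47.5% | 4.8% |
| 20% | 3.0 | 45.0% | 9.1% |
| 30% | 4.5 | 42.5% | 13.0% |

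Replacement to 3:3 restores the counts but not the composition of the arms.

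**Step 5. Would barring re-entry be enough?** For illustration, assume no device effect, an SAE risk of 30% in patients who would start and 60% in those who would not, and SOC patients counted in the safety population.

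With one redraw:
- q = 10%: SOC (0.5 x 0.33 + 0.025 x 0.6)/0.525 = 34.3%; DIALIVE (0.45 x 0.3 + 0.025 x 0.6)/0.475 = 31.6%; gap 2.7 points.
- q = 20%: SOC (0.5 x 0.36 + 0.05 x 0.6)/0.55 = 38.2%; DIALIVE (0.40 x 0.3 + 0.05 x 0.6)/0.45 = 33.3%; gap 4.8 points.

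With no re-entry, but never-treated DIALIVE patients left out as section 6 requires:
- q = 10%: SOC 0.9 x 0.3 + 0.1 x 0.6 = 33%; DIALIVE 30%; gap 3.0 points.
- q = 20%: SOC 0.8 x 0.3 + 0.2 x 0.6 = 36%; DIALIVE 30%; gap 6.0 points.

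Barring re-entry alone therefore leaves a false gap, slightly larger than with a redraw. Only a comparison by first allocation of all randomised patients removes it: both arms then show 33%, or 36%.

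**The case against.** The best defence is that the protocol never says such a patient is randomised again, that the study is descriptive with no hypothesis test, and that safeguards exist. Re-entrants must meet every criterion again, reasons for screen failure are documented (5.3.3), screen failures are followed for at least 28 days (2.2), and the database is meant to prevent duplicate entries (7.1.2). Appendix 7 accounts for 14 enrolled patients (8 DIALIVE, 6 SOC). It mentions two DIALIVE patients who did not complete the minimum treatment, but no non-starter or re-entrant.

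Much of this stands, and it rules out several stronger readings that a reader might infer:

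- **That unstable patients are moved to SOC, so the device looks safer.** Re-entry needs fresh eligibility, and the criteria exclude haemodynamic instability, respiratory failure, more than three organ failures, INR above 3 and low platelets. Re-entrants have survived and requalified; their risk may be higher or lower. Under the illustrative risks above, the redraw slightly narrows the gap.
- **That the chance of SOC rises to 75%.** The sum 0.5 + 0.5 x 0.5 is the chance before the first draw for a patient whose DIALIVE allocation would lapse once and who always requalifies. After a lapse the figure is 50% under simple 1:1, and filling cohorts to 3:3 may change even that.
- **That the SAE percentage shifts by up to 20 points.** 3/15 needs three non-starters, all redrawn to SOC (0.5 x 0.5 x 0.5 = 0.125) and all moving the count the same way.
- **That one person holds two overlapping records.** Section 2.2 does not say when the 28 days begin. Overlap is possible but not established.
- **That no SOC patient can become a screen failure after allocation.** The first kind of screen failure is limited neither to one arm nor expressly to the time before randomisation. What is specific to DIALIVE is the start deadline.
- **That sites would let Day 1 lapse on purpose.** Nothing in the document shows this.

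The defence does not remove the rule itself. Descriptive percentages by arm still need comparable arms, and Appendix 7 does not show whether relabelled patients were among the 14.

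**Conclusion.** The point holds in a limited form. Section 2.2 returns an enrolled, randomised DIALIVE patient to screening because of an event after allocation. The re-entry route most naturally carries a second allocation, and the protocol does not say otherwise. The trigger exists in one arm of an open-label trial, which conflicts with the purpose of randomisation stated in section 4.2.

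The harm is to the comparability of the arms, not to a type I error rate. Its frequency and direction are unknown. The firm figures are the weight of one patient: 6.7 points of an arm overall and one third of an arm within a cohort. The shares and gaps in the working rest on assumed non-start rates, assumed SAE risks and a flat 50% second draw, and only illustrate the mechanism. Under those assumptions, leaving never-treated DIALIVE patients out of the safety population is enough by itself to create the gap, so the rule and the analysis need to be corrected together. In a descriptive first-in-man study this is a should-fix.

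**What to change.** 1. In section 2.2, limit screen failure to patients who fail before randomisation, and remove re-entry for randomised patients.
2. State that each patient is randomised once. A DIALIVE patient who has not started by the end of Day 1 keeps the original allocation and subject number, is recorded as randomised but not treated, and is followed as scheduled.
3. Have the IWRS refuse a second randomisation of the same person.
4. Report any re-entry that has already occurred, with the first and any later allocation. Section 5.3.8 expects recruitment to run only until December 2019, so this may be the most useful step.
5. Beside the safety population of section 6, add a between-arm SAE summary by first allocation for all randomised patients, including non-starters.

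These changes concern allocation and counting only; they leave the clinical rules on starting dialysis untouched.

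The cost is some protocol wording, one IWRS check and one extra table. A non-starter can no longer be recycled as a new subject, so a cohort slot may need one further patient, which section 5.1.7 already allows.

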Commencement of DIALIVE treatment session i.e. connection of patient to the Prismaflex machine = time point 0, can occur at any time before the end of study Day 1 subject to availability of all relevant information required for treatment to commence. All blood samples should be measured from this time point. Any pre samples required should be taken just before connection.

Nuts and bolts of DIALIVE Treatment: a ready reference

-Before starting treatment

The patient to be moved to an intensive care unit or similar once randomised to DIALIVE. Appropriate monitoring needs to be instituted including the following:

- Insertion of an arterial line for continuous invasive blood pressure monitoring and blood sampling
- Insertion of a vascular catheter for DIALIVE treatment
- Insertion of a central venous catheter for prompt treatment with vasopressors if required (Lines should be inserted under USS guidance. Correction of clotting abnormalities, if any, should follow local protocols. The line positions should be confirmed through appropriate means; e.g. CXR for neck lines).

 * NB: Majority of ACLF grade 3 patients are likely to be already in the ICU with the above monitoring in situ.

Additional tests (Baseline samples for FBC, U/E, LFT, coagulation, septic screen will already have been collected to check eligibility) prior to commencing DIALIVE therapy will be done:

Arterial blood gas analysis

- Haemolysis screen (FBC including reticulocyte count, blood film, unconjugated and conjugated bilirubin, LDH, haptoglobin, urinary free haemoglobin) – to be performed only on D1, before and after therapy
- DIC screen, if clinically indicated
- And, Endotoxin Activity Assay (EAA) analysis (start of day 1, 2 and 3)
- Blood to be collected as part of biobank samples.(start of day 1, 2 and 3)

Fluid pre-loading of up to 500mls over 1-2 hours is implemented, the volume and speed of fluid therapy to be determined on a clinical basis, and the choice of fluid would preferably be albumin (4.5 or 5% solution as per local availability).

- during dialysis session

- Anticoagulation with unfractionated heparin and/or prostacycline analogues (the dose as per local protocols)
- Blood flow rates on DIALIVE device to be started at 50 mls/min and increased gradually over 1-2 hours to up
 to a maximum of 250 mls/min

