5.1.3 Secondary End Points

To evaluate the performance of the DIALIVE in patients with ACLF. This is measured by;

Change in Plasma endotoxin level (endotoxin activity and concentration) between;

D1, D3, D5 and D10 across SOC arm $\,$

D1, D3, D5 and D10 across DIALIVE arm

_

¹⁰ In case a patient's treatment is discontinued, the follow up period will remain 28 days from the moment of randomization.

Clinical Investigation Plan	CIP YAQ-002	Version: 7.0 10 October 2019
-----------------------------	-------------	------------------------------

Start and end of a treatment session (on D1, D2 and D3) with DIALIVE D1,D3, D5 and D10 between SOC and DIALIVE arms for patients presenting with the same grades of ACLF (i.e. Grade 1 ALCF compared with Grade 1 ACLF)

Target-Value (TV): 40% reduction; Acceptable-Value (AV): 20% reduction at end of treatment cycle.

• Change in Albumin function (Human non-mercapt albumin -2 (HNA-2) / Human marcapt albumin (HMA) ratio:

D1, D3, D5 and D10 across SOC arm
D1,D3, D5 and D10 across DIALIVE arm
Start and end of a treatment session (on D1, D2, D3) with DIALIVE
D1,D3, D5 and D10 between SOC and DIALIVE arms for patients presenting with the same grades of ACLF (i.e. Grade 1 ALCF compared with Grade 1 ACLF)

TV: 40% reduction; AV: 20% reduction at end of treatment cycle.

- Mortality: 28-days and 90 days
- Change in ACLF Grade
- Change in CLIF-ACLF score
- Improvement in individual organ function: Brain (HE), Kidney (creatinine), CVS (mean arterial pressure), Pulmonary (P/F ratio, or S/F if patient is not intubated), Liver (serum bilirubin) and coagulation (INR and platelets).
- Status at ICU and Hospital Discharge (including discharge to a hospice for palliative care).
- Lengths of stay in ICU and Hospital at D28 and D90
- ICU and Hospital re-admissions with another episode of ACLF up to 3 months after randomisation.

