36 Pre-treatment is prior to initiating DIALIVE treatment. Post-treatment is within one hour after ending a DIALIVE treatment session)
37 Urine Biomarker tests: NGAL, TLR4, IL-18
38 Effluent is collected from the effluent line and from the waste collection bags.

³⁹ Haemolysis screen: FBC including reticulocyte count, blood film, unconjugated and conjugated bilirubin, LDH, haptoglobin and urinary free haemoglobin only at end of DAY

safety of DIALIVE treatment

Follow Up

period

Clinical Investigation Plan CIP YAQ-002 Version: 7.0 10 0	October 2019
---	--------------

5.4.1. Additional sponsor representative(s) activities (excluding monitoring).

Sponsor representatives will be available to assist sites in the device set up.

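### The protocol does not clearly place the DIALIVE Day 1 biomarker baseline before or after the DIALIVE-only fluid preload; read literally, it falls after

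*Protocol*

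**What the plan says.** All references are to the protocol.

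- **Time zero and pre samples (2.2, Definitions).** Treatment begins at connection: "connection of patient to the Prismaflex machine = time point 0". For samples the rule is: "Any pre samples required should be taken just before connection".
- **Preload (2.2, ready reference, steps before starting treatment).** "Fluid pre-loading of up to 500mls over 1-2 hours is implemented, the volume and speed of fluid therapy to be determined on a clinical basis". On the fluid: "the choice of fluid would preferably be albumin (4.5 or 5% solution as per local availability". Albumin is therefore preferred but not required, and 500 ml is a ceiling.
- **Samples in the same list.** The endotoxin activity and biobank draws stand above the preload sentence: "And, Endotoxin Activity Assay (EAA) analysis (start of day 1, 2 and 3" and "Blood to be collected as part of biobank samples.(start of day 1, 2 and 3".
- **Footnote 36 (5.4).** "Pre-treatment is prior to initiating DIALIVE treatment". It does not mention the preload.
- **Arms (5.4).** The preload appears in the DIALIVE during-treatment table and not in the SOC schedule. SOC patients may still receive fluid and albumin where indicated (2.1, 2.2, 3.4).
- **Endpoints (5.1.3).** Changes in endotoxin (activity and concentration) and in HNA-2/HMA are described over D1, D3, D5 and D10 within each arm and between arms at the same ACLF grade. In the DIALIVE arm they are also described from start to end of each session. The thresholds, set for both biomarkers, are: "TV: 40% reduction; AV: 20% reduction at end of treatment cycle".

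**The concern.** Day 1 is the first point of the D1-D3-D5-D10 series in both arms. A sample drawn before a 1-2 hour infusion is hard to describe as drawn just before connection. A site that follows both instructions literally therefore takes the DIALIVE Day 1 sample after the preload. The SOC Day 1 sample has no such step before it, so change from baseline would start from different states in the two arms.

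Because the volume and the fluid are left to clinical judgement, and sites could reasonably follow either order, the baseline could also differ between sites within the DIALIVE arm. Endotoxin and albumin function are the study's stated performance measures (synopsis, 5.1), and about 15 evaluable patients per arm are planned. If the sampling order and the preload are not recorded, a descriptive analysis cannot recover them later. Section 2.2 also asks for a new baseline after a break of more than 24 hours, so the question recurs if a cycle restarts.

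**Working it through.** **Step 1: what the visible text fixes.** Four places bear on the order.

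| Place | Order of sample and preload |
|---|---|
| 2.2, pre-sample rule | Just before connection, so after the preload if read literally |
| 2.2, ready-reference list | Samples listed above the preload, which suggests the reverse; the list is not said to be a sequence |
| 5.4, footnote 36 | Fits either order |
| Appendix 8, illustration of a session | Figure not shown; it may settle the order |

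The only explicit timing rule favours sampling after the preload. The other visible places do not confirm it.

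**Step 2: size for endotoxin concentration.** The protocol states no figure for this, so there is nothing to reproduce. The preload volume V = 0.5 L (the ceiling) comes from 2.2. Plasma volume PV = 2.5-5.0 L and the retained share r = 1 or 0.5 are assumptions.

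- Baseline factor: f = PV / (PV + V × r)
- Fall in baseline: 1 - f
- Reading of a true reduction t, if the fluid has gone by the later sample: 1 - (1 - t) / f

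| PV | Retained | f | Baseline fall | True 20% reads as | True 40% reads as |
|---|---|---|---|---|---|
| 2.5 L | 500 ml | 2.5/3.0 = 0.833 | 16.7% | 4.0% | 28.0% |
| 5.0 L | 500 ml | 5.0/5.5 = 0.909 | 9.1% | 12.0% | 34.0% |
| 2.5 L | 250 ml | 2.5/2.75 = 0.909 | 9.1% | 12.0% | 34.0% |
| 5.0 L | 250 ml | 5.0/5.25 = 0.952 | 4.8% | 16.0% | 37.0% |

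The last two columns need both conditions: fluid present at baseline and gone at follow-up. If the later sample is equally diluted, the factor cancels. With no preload, or with a sample drawn before it, f = 1 and 20% reads as 20%.

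**Step 3: HNA-2/HMA.** This is a ratio of two fractions in the same plasma, so simple dilution cancels. Mixing with infused albumin need not cancel. A full 500 ml of 4.5-5% solution carries 500 × 0.045 = 22.5 g to 500 × 0.05 = 25 g. A session at 5 g/hr for 8-10 hours gives 40-50 g, so a full albumin preload is 22.5/50 = 45% to 25/40 = 62.5% of the session amount. The shift in the ratio depends on the composition of the product and of the patient's albumin. The protocol gives neither; if the two match, the shift is zero.

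**Step 4: endotoxin activity.** The protocol gives no relation between the assay reading and dilution, so no size can be derived.

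**The case against.** The strongest reply is that no sentence orders the sample against the preload. The list order points to sampling first. The missing Appendix 8 figure, which the amendment history says was added to help sites sample correctly, may show the order. The same history refers to a Laboratory Manual, which is also not shown. This stands: a reader might infer that the DIALIVE baseline is always drawn after an albumin preload, and the documents do not support that. Volume is discretionary up to 500 ml and albumin is only preferred.

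Three further inferences are tempting and go too far.

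- *Both biomarkers are biased by about the 20% Acceptable Value.* For endotoxin concentration the range is 5-17% under the assumptions above, at the maximum volume, and its effect on measured change depends on the fluid having left by follow-up. For HNA-2/HMA no size can be given.
- *The flaw flatters the device.* For endotoxin concentration the direction is the opposite: a lowered baseline makes the DIALIVE reduction look smaller.
- *SOC starts from an untreated baseline.* SOC patients may have had fluid or albumin where indicated. Only the protocol-scheduled preload is specific to DIALIVE.

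A fair point also concerns the thresholds. They are set at the end of the cycle. If a preload precedes each of three sessions, a single pre-preload baseline would credit up to 3 × 500 ml = 1.5 L of fluid, and up to 3 × 22.5 = 67.5 g to 3 × 25 = 75 g of preload albumin, to the device. A just-before-connection baseline isolates the device better. Which one the thresholds should use is a choice the protocol should state, not an error in either direction.

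What survives is the ambiguity, together with a literal reading that makes the arms' Day 1 samples unlike each other.

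**Conclusion.** The point holds as an unfixed sampling order whose literal reading puts the DIALIVE Day 1 baseline after an arm-specific step. It is not shown that every baseline is altered.

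If a full preload precedes the sample, baseline endotoxin concentration would be about 9-17% lower with full retention and 5-9% lower with half retention, on an assumed plasma volume of 2.5-5 L. That is large enough to matter against the 20% and 40% thresholds. It understates the DIALIVE change to Day 5 or 10 only if the fluid has gone by then. On Day 3 a repeated preload could cancel part of it. For HNA-2/HMA and for endotoxin activity, the size cannot be worked out from the protocol.

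The endpoints concerned are secondary and descriptive, with no tests planned. The primary safety endpoint and the sample size are untouched. This is a cheap improvement worth making, not a threat to the trial's main conclusion.

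**What to change.** In 2.2 and footnote 36:

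1. State that the DIALIVE Day 1 biomarker and endotoxin activity baseline, used for the D1-to-D3, D5 and D10 changes and for the between-arm comparison, is drawn before the preload starts.
2. Keep the just-before-connection sample as the start-of-session value for change within a session, so that preload dilution is not counted as a device effect there.
3. State which of the two samples the Target and Acceptable Values use.
4. Record the preload fluid, volume and time, and the time of each sample.

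Align Appendix 8 and the Laboratory Manual with this wording. The preload itself is not changed.

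Cost: a wording change, a few recorded fields, and at most one extra blood draw and endotoxin activity assay per DIALIVE patient at the first session of a cycle. Section 2.2 already requires an arterial line for blood sampling before treatment.
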